3.1.3 Cohort Escalation

A partially parallel cohort progression design will be used for this study, with collection, compilation, and assessment by the External Safety Monitoring Committee (ESMC) of a total of 7 days of safety and laboratory data from the preceding single or concurrent cohorts required prior to enrolling in the subsequent cohort(s). In this schema, Cohort 1 will be enrolled first and all subjects in Cohort 1 will be followed for safety for 7 days prior to enrollment in any subsequent cohort(s). Cohort progression will occur after review of all cumulative safety data, including safety laboratory data (but not including immunogenicity data) by the MedImmune medical monitor, who will review only blinded data, and the ESMC, who will review blinded data and can choose to also review unblinded data. The principal investigators are invited to the open session for blinded review of data. External Safety Monitoring Committee review of cohort progression is described in [Section 4.8.5](#). If there are no safety concerns, Cohorts 1a and 2 may enroll at the same time. After all subjects in those cohorts have been followed for 7 days, Cohorts 2a and 3 will be enrolled in the same

fashion. After all subjects in Cohorts 2a and 3 have been followed for 7 days, Cohort 3a will be completed.

Cohort expansion will occur at the recommendation of the ESMC as described in Section 4.4.1. If cohort expansion occurs, a total of 12 subjects will be added to the expanded cohort with the same randomization ratio (5:1) applied.

3.1.4 Management of Study Medication-related Toxicities

Toxicities related to vaccine administration will be treated in accordance with best medical practices for the observed event.

3.2 Study Design and Dose Rationale

The study will be randomized, placebo-controlled, and double-blind to ensure a robust design and minimize bias.

The sample size for this study is selected to support the assessment of the safety of MEDI7510.

Both antibody and cell-mediated immunity are considered to be important to the immune response in the target population of older adults, with the adjuvant expected to provide for the cell-mediated responses that would not be expected from RSV sF alone and also to contribute to the duration of antibody responses. Thus, after the initial safety of a dose of RSV sF has been assessed, that dose will be assessed in combination with a low dose of adjuvant. An antigen dosage that maximizes humoral and cell-mediated immune responses and that is safe and tolerable will be selected for further study.

Subjects will be followed for 360 days after dosing both to assess the long-term safety of the antigen and adjuvant combination and to permit assessment of the duration of the immune response.

3.2.1 Dose Rationale

Starting doses of 20 µg of RSV sF initially alone and then, as MEDI7510, with 2.5 µg GLA in 2% (w/v) SE are proposed for the Phase 1a single-dose study based on FTIH dosing considerations. The 2.5 µg dose of GLA in combination with 2% (w/v) SE was selected to be a low dose based on FTIH dosing considerations but to be high enough to permit assessment of adjuvant effect on immune responses and to support selection of a dose of antigen to be assessed with ascending doses of GLA-SE in a subsequent Phase 1b study. These proposed initial doses provide safety factors of > 130-fold for the antigen dose and > 60-fold for the

adjuvant dose compared to the NOAEL for systemic toxicities observed in the Good Laboratory Practice (GLP) toxicity studies in animals, based on a human equivalent dose comparison. The highest dose of MEDI7510 to be tested in this Phase 1a protocol will be 80 µg RSV sF with 2.5 µg GLA in 2% (w/v) SE. The GLP toxicity study found no significant safety issues at a dose of 90 ± 12 µg RSV sF with 5 µg GLA in 2% (w/v) SE, the highest dose tested; therefore, safety margins for humans, based on body weight comparisons, were approximately 110-fold in the rat. These studies conservatively support single clinical doses of up to 80 µg RSV sF with 5 µg GLA in 2% (w/v) SE.

3.2.2 Rationale for Study Population

The subject population selected for this FTIH study is that of older adults, a group that will be the target of efficacy studies of this vaccine because older adults are at greater risk of medically significant RSV disease than younger adults. Older adults also have been shown to have an immune response to RSV that differs from that of younger adults in that, while their antibody levels are similar to those of younger individuals, they have lower cell-mediated immune responses ([Cherukuri et al, 2013](#)).

A population of older adults that is generally healthy or that has stable, chronic underlying medical conditions was selected for this FTIH study, because enrolling adults ≥ 60 years of age who are completely healthy did not appear feasible and, in addition, would skew the enrollment population towards those closer to 60 years of age. Subjects with any history of autoimmune disorder will be excluded from this FTIH study because some subjects will receive adjuvant. Immunosuppressed subjects will also be excluded because they would be expected to have altered immune responses to vaccines. Finally, in the absence of any data on local site reactions, subjects with a history of thrombocytopenia or bleeding disorder will be excluded from this FTIH protocol. These older adults are an acceptable study population for this FTIH study from a safety perspective, and a preferred study population from an immunological perspective, because they represent the target population for the MEDI7510 vaccine. Younger adults do not have deficient cell-mediated immune responses and thus would not provide data for dose selection in older adults ([Cherukuri et al, 2013](#)). Older adults with more complicated medical problems, although ultimately planned for inclusion in future studies, will not be included in this FTIH study both to enhance the safety of the subjects and to provide a clearer assessment of vaccine safety.

3.2.3 Rationale for Endpoints

The primary endpoint for this study is intended to assess the safety and tolerability of single ascending IM doses of RSV sF antigen and MEDI7510 in adults ≥ 60 years of age who are

healthy or who have stable, chronic underlying medical conditions. Local and systemic solicited symptoms occurring during the week post dosing are important measures of tolerability. Adverse events and SAEs temporally associated with dosing will be collected to assess safety. Longer term evaluation will assess events, including SAEs, NOCDs, and AESIs, that may warrant increased follow-up in an adjuvanted vaccine.

The secondary endpoints are designed to assess both humoral and cell-mediated immunity. Humoral immunity will be assessed by a microneutralization assay for RSV A and an RSV F-specific IgG antibody assay. Cellular immunity will be measured by an RSV F peptide pool IFN γ ELISPOT assay, an assay selected for sensitivity and reproducibility.

4 MATERIALS AND METHODS

4.1 Subjects

4.1.1 Number of Subjects

Approximately 144 subjects will be enrolled at approximately 3 study centers in the US.

4.1.2 Inclusion Criteria

Subjects must meet *all* of the following criteria:

1. Age \geq 60 years at the time of screening
2. Written informed consent and any locally required authorization (eg, Health Insurance Portability and Accountability Act [HIPAA]) obtained from the subject prior to performing any protocol-related procedures, including screening evaluations
3. Ambulatory or ambulatory with assistance (not institutionalized, bedridden, or homebound)
4. Weight \geq 110 lbs (\geq 50 kg)
5. Hemoglobin within normal range for age and gender
6. Subject available by telephone
7. Subject able to understand and comply with the requirements of the protocol, as judged by the investigator
8. Subject able to complete follow-up period of 360 days after dosing as required by the protocol

4.1.3 Exclusion Criteria

Any of the following would exclude the subject from participation in the study:

1. History of allergy to any component of the vaccine

2. Pregnancy or potential to become pregnant during the study. Females who (1) have had a menstrual period within the 12 months prior to study enrollment or (2) are undergoing any fertility treatment or who plan to undergo fertility treatments during the study period are excluded
3. Any unstable chronic medical condition, including one that has resulted in change in therapy (medication or other) in the 30 days prior to randomization or hospitalization in the previous year or might be predicted to result in hospitalization in the year after enrollment. Subjects with severe, untreated or uncontrolled underlying medical disease that might either compromise subject safety or affect the ability to assess safety of the investigational product are excluded
4. Clinically significant abnormalities in screening laboratory assessments or screening electrocardiogram (ECG), according to the judgment of the investigator
5. History of hepatitis B or hepatitis C infection
6. Cognitive disorder such that informed consent cannot be obtained directly from the subject
7. Previous vaccination against RSV
8. History of allergy to eggs in adulthood
9. History of or current autoimmune disorder (stable, treated hypothyroidism caused by Hashimoto's thyroiditis is acceptable)
10. Immunosuppression caused by disease, including human immunodeficiency virus (HIV) infection, or medications. Any oral prednisone dosing within 30 days of enrollment or planned dosing within the 360-day follow-up period would disqualify. Topical, intranasal, inhaled, or intra-articular corticosteroids do not disqualify. Expected need for immunosuppressive medications during the 360-day follow-up period would disqualify
11. History of splenectomy or of condition affecting splenic function (eg, hemoglobinopathy)
12. History of cancer within preceding 5 years other than treated non-melanoma skin cancer
13. Body mass index (BMI) ≥ 40
14. Significant infection or other acute illness, including fever $\geq 100^{\circ}\text{F}$ ($\geq 37.8^{\circ}\text{C}$) on the day prior to or day of randomization
15. Receipt of any nonstudy vaccine within 30 days prior to study dosing or expected receipt of nonstudy vaccine within 30 days after study dosing
16. Receipt of any investigational product in the 90 days prior to randomization or expected receipt of investigational product during the period of study follow-up
17. Receipt of immunoglobulins or blood products within 4 months of study dosing (120 days) or expected receipt of investigational product during the period of study follow-up
18. History of thrombocytopenia or bleeding disorder or use of anticoagulants such as warfarin, heparin/low molecular weight heparin, thrombin inhibitors (dabigatran and others), or factor Xa inhibitors (rivaroxaban, apixaban, and others). Subjects receiving drugs with anti-platelet activity such as nonsteroidal antiinflammatory drugs, clopidogrel or aspirin are not excluded.

19. Expected receipt of antipyretic or analgesic medication on a daily or every other day basis from randomization through 72 hours after receipt of investigational product (Note: A daily dose of ≤ 163 mg of aspirin is not considered a contraindication to enrollment.)
20. Subjects who have significant scarring, tattoos, abrasions, cuts, or infections over the deltoid region of both arms that, in the opinion of the investigator, could interfere with evaluation of injection site local reactions.
21. Any condition that, in the opinion of the investigator, would interfere with evaluation of the investigational product or interpretation of subject safety or study results
22. Concurrent enrollment in another clinical study that involves any invasive clinical procedure, including phlebotomy.
23. History of alcohol or drug abuse or psychiatric disorder that, in the opinion of the investigator, would affect the subject's safety or compliance with study
24. Employees of individuals directly involved with the conduct of the study, individuals who themselves are involved with the conduct of the study, or immediate family members of such individuals

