4.7.2 Prohibited Concomitant Medications

Use of new concomitant medications including over-the-counter medications, herbal supplements, and new vitamins from Day 1 through Day 28 is discouraged; in particular, use of pain or anti-inflammatory agents is discouraged because of the possibility of masking reactions to the study vaccines.

The following medications or medical procedures are not permitted. The sponsor must be notified if a subject receives the following medications or undergoes any of the following medical procedures:

1. Any vaccine, whether licensed or investigational, between randomization and 30 days post dose
2. Any investigational product between randomization and collection of the Day 361 post dose blood sample
3. Glucocorticoids at a dose ≥ 20 mg/day of prednisone equivalent given daily or on alternate days for ≥ 14 consecutive days between randomization and collection of the Day 361 post dose blood sample

4. Other systemically administered drugs with significant immunosuppressive activity, such as azathioprine, tacrolimus, cyclosporine, methotrexate, or cytotoxic chemotherapy between randomization and collection of the Day 361 post dose blood sample
5. Systemic radiation therapy between randomization and collection of the Day 361 post dose blood sample
6. Immunoglobulin or blood products between randomization and collection of the Day 361 post dose blood sample

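### The second clause of exclusion 17 repeats exclusion 16, so expected receipt of immunoglobulins or blood products is not explicitly excluded although Section 4.7.2 prohibits it

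*Protocol*

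**What the plan says.** Two adjacent exclusion criteria in Protocol Section 4.1.3 are involved. Item 16 reads "Receipt of any investigational product in the 90 days prior to randomization or expected receipt of investigational product during the period of study follow-up". Item 17 begins "Receipt of immunoglobulins or blood products within 4 months of study dosing (120 days) or expected receipt of investigational product" and closes with the same follow-up window. The shared ending is "or expected receipt of investigational product during the period of study follow-up".

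Section 4.7.2 (Prohibited Concomitant Medications) introduces its list with "The following medications or medical procedures are not permitted" and requires the sponsor to be told of any breach. Item 6 of that list is "Immunoglobulin or blood products between randomization and collection of the Day 361 post dose blood sample".

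The secondary humoral endpoints in Section 2.2.2 are RSV A neutralizing antibody and anti-F IgG: titers, fold rises and the share of subjects with at least a 4-fold rise from baseline, through Day 361.

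**The concern.** Item 17 starts by looking back 120 days for one class of product and then looks forward for a different class, which item 16 already covers. The forward-looking half that the sentence seems meant to carry is missing. Read literally, a subject with an immunoglobulin infusion or transfusion already planned for the follow-up year meets no named exclusion, although receiving that product would breach Section 4.7.2.

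At stake is the serum antibody evidence. The results feed the interim analysis in Section 4.8.6, which informs the choice of antigen dose for Phase 1b. A breach would come to light only after dosing, and Section 4.1.7 provides for replacing subjects who were not dosed or who drop out before Day 28, not those who stay in the study after a prohibited product. Screening is the point at which the problem can be prevented.

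**Working it through.** The check is mainly a comparison of text. The protocol gives no figure of its own on this point to reproduce.

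**Step 1: the two criteria, clause by clause.**

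| Item | Past clause | Expected clause |
|---|---|---|
| 16 | investigational product, 90 days | investigational product, follow-up period |
| 17 | immunoglobulins or blood products, 120 days | investigational product, follow-up period |

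The two expected clauses are identical. In item 17 the clause adds nothing to item 16.

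**Step 2: the protocol's own pattern.** Where Section 4.1.3 pairs past with expected exposure, it elsewhere keeps to one class:
- Exclusion 10 covers oral prednisone both before enrollment and as planned later, and adds "Expected need for immunosuppressive medications during the 360-day follow-up period would disqualify".
- Exclusion 15 covers non-study vaccine received before dosing and "expected receipt of nonstudy vaccine within 30 days after study dosing".
- Exclusion 16 covers investigational product in both directions.

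Item 17 is the one that changes class midway. That points to a copying slip rather than a choice.

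**Step 3: eligibility against the prohibited list.** Vaccines, investigational product, glucocorticoids and other immunosuppressants (Section 4.7.2 items 1 to 4) each have a forward-looking exclusion. Immunoglobulin and blood products (item 6) have only the look-back. Systemic radiation (item 5) is not named in the eligibility criteria at all, so the match between the two lists is not complete elsewhere either. Item 17 differs in that it contains a forward-looking clause, and that clause names the wrong product.

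**Step 4: what else could exclude such a subject.**
- By judgment: inclusion 7 (able to comply, as the investigator sees it), exclusion 3 (unstable condition or predicted hospitalization) and exclusion 21 (a condition that would interfere with evaluation or interpretation). None names these products.
- By reducing the number of candidates: the 120-day look-back in item 17 itself, normal hemoglobin (inclusion 5), and thrombocytopenia, bleeding disorder or anticoagulant use (exclusion 18).

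**Step 5: size, under an assumption.** The protocol does not say that these products would alter the assays. Assume that donor antibody could change one subject's seroresponse status at one visit:
- Active arm, n = 20 (Table 3.1.2-1): 1/20 = 0.05, or 5 percentage points.
- Pooled placebo, 6 cohorts × 4 = 24: 1/24 = 0.042, or about 4 percentage points.

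How many subjects would be exposed, and how likely a change of status would be, cannot be derived from the document.

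**The case against.** The best case on the other side is that almost nobody falls through the gap. Anyone on regular immunoglobulin or transfusion at intervals shorter than 120 days is caught by the first clause of item 17. Many other likely recipients are removed by the hemoglobin, autoimmune, immunosuppression, spleen, cancer and bleeding criteria. Inclusion 7 is mandatory, and a subject with a prohibited product already planned cannot properly be judged able to comply. Prohibited medications are also asked about through Day 361, so receipt should be detected, and its handling in analysis can be left to the SAP. The analyses are descriptive, and these endpoints are secondary to safety.

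Most of this stands, and it limits the impact. It does not repair the criterion: inclusion 7 works only if the investigator makes the connection, and an analysis rule cannot change who was enrolled.

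A reader might infer more than the text supports:
- **That such subjects are plainly eligible and certain to breach the protocol.** They are only not explicitly excluded; the judgment-based criteria still apply.
- **That a single exposure would produce a 4-fold rise.** Nothing in the protocol shows this.
- **That all six post-dose humoral visits would be affected.** Even if the protocol's 120-day look-back is taken as the period of concern, one receipt soon after dosing spans Days 29, 61 and 91, which is three visits.
- **That donor antibody would mimic wild-type RSV infection through the anti-Ga, anti-Gb or anti-N assays.** The protocol does not show this. A subject so classified would also leave the immunogenicity cohort under Section 4.8.6, and so could not add to the seroresponse rate as well.

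**Conclusion.** Wrong as written, low impact. The duplication, and its mismatch with Section 4.7.2 item 6, are certain from the text. Neither redaction nor the change log explains them, and Administrative Change 1, which was issued partly to correct typographical errors, left them in place. Few subjects are likely to be affected. The figure of 5 percentage points is the effect of one changed responder in one active arm, not an expected bias. It rests on the assumption about donor antibody, which is a reasonable inference from the prohibition, the look-back and the serum endpoints but is not stated in the protocol. The primary safety endpoint is not called into question.

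**What to change.** Reconcile exclusion 17 with Section 4.7.2 item 6 by having its second clause refer to expected receipt of immunoglobulins or blood products, the same class as its first clause, with the follow-up window left as it is. Exclusion 16 already covers expected investigational product, so nothing is lost. Update the eligibility checklist to match. The cost is one phrase in the protocol and one checklist line, with no added visit, sample or subject.

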4.1.4 Subject Enrollment and Randomization

Study participation begins (ie, a subject is “enrolled”) once written informed consent is obtained. Once informed consent is obtained, a subject identification (SID) number will be assigned by an interactive web response system (IWRS), and the screening evaluations may begin to assess study eligibility (inclusion/exclusion) criteria. The SID number will be used to identify the subject during the screening process and throughout study participation, if applicable.

A master log of all consented subjects will be maintained at the site and will document all screening failures (ie, subjects who are consented but do not meet study eligibility criteria and/or are not randomized), including the reason(s) for screening failure.

Subjects who fail to meet the inclusion/exclusion criteria (ie, screening failures) should not be randomized or receive investigational product. These subjects may be reconsidered for enrollment if failure was due to a time-limited exclusion as long as the subject continues to meet all other eligibility criteria. Subjects who failed to meet laboratory or ECG criteria may not be enrolled based on repeated testing unless original testing resulted in laboratory error. Rescreening of the same subject is permitted if randomization did not occur within 30 days of screening, as described in Section [4.2.1](#).

4.1.5 Withdrawal from the Study

Subjects are free to withdraw from the study at any time (investigational product and assessments), without prejudice to further treatment (withdrawal of consent). Subjects who

withdraw from the study will always be asked about the reason(s) for withdrawal and about the presence of any AEs. If possible, subjects who withdraw consent will be seen and assessed by the investigator. Adverse events will be followed up; diary cards should be completed and returned by the subject. If a subject withdraws consent from all further participation in the study, then no further study visits or data collection should take place. Subjects who withdraw consent for phlebotomy but not for safety follow-up should continue to be followed for safety events in accordance with the protocol. Telephone contacts may be substituted for face-to-face visits in these subjects.

4.1.6 Discontinuation of Investigational Product

Because this is a single dose vaccine study, discontinuation of investigational product does not apply.

4.1.7 Replacement of Subjects

Subjects who are randomized but not dosed may be replaced. At the discretion of the sponsor or at the recommendation of the ESMC, subjects who drop out of the study for reasons other than safety before Day 28 may also be replaced. The replacement subject will receive the same treatment assignment as the corresponding subject being replaced.

